5.3. Stage II Procedure – Permanent Device Implantation

During Stage II, the patient will undergo implantation of the permanent sacral neuromodulator, InterStim, if symptoms showed 50% improvement during the test phase. This will require a 2-3 day stay in the hospital and will be performed under general anesthesia.

5.4. Three Month Follow up Visit

At the time of this visit, patients who did receive the implanted InterStim will receive an additional \$50 Prepaid gift card for undergoing CPT Testing and filling out surveys at the 3 month follow up visit.

5.4.1. Questionnaires and Surveys Administered

- 5.4.1.1.** Pelvic Floor Distress Inventory (PFDI-20)³³
- 5.4.1.2.** Fecal Incontinence Severity Index (FISI)³⁴
- 5.4.1.3.** Pelvic Organ Prolapse Incontinence Sexual Questionnaire, IUGA-revised (PISQ-IR)³⁵:
- 5.4.1.4.** Golombok Rust Inventory of Sexual Satisfaction (GRISS)³⁶:
- 5.4.1.5.** 3-day urinary and 7-day bowel diary
- 5.4.1.6.** Fecal Incontinence Quality of Life questionnaire (FiQOL)

5.1.4.2. Other Examinations Performed

- 5.1.4.2.** Current Perception Threshold (CPT) Testing

6.0. STATISTICAL PLAN

6.1. Statistical Analysis:

Each sensory modality threshold as determined at each of the different anatomic sites will be evaluated separately. Sensory thresholds will be compared before and after SNM placement using paired t-test. Multivariate regression models will be used to determine clinical and neurophysiologic predictors of symptom improvement. Urethral sphincter volumes and presence/absence and size of internal and external anal sphincter defects will be compared in responders and non-responders.

6.2. Sample Size Determination:

The sample size estimate was based off data from our prior work and urethral CPT in women with overactive bladder symptoms before and after treatment of tolteradine . Assuming a mean urethral CPT of 1.3 at 250 Hz prior to treatment and a mean of 0.75 after treatment with a standard deviation of 0.66 we estimate that 13 subjects are needed to show a significant difference with a 80% power at 5% significance level. Assuming a 20% dropout rate, we will recruit 15 women and their partners.

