1.2.2 Pathophysiology of UUI/FI and Mechanism of Action of SNM

The etiologies of UUI and FI are complex and likely multifactorial; however, increasing data suggests neuromuscular dysfunction, particular alterations in afferent nerves, plays a role in both. SNM has proven effective for treatment of UUI and FI^{11,12}. Electrical stimulation is thought to modulate afferent nerves and reflex pathways, which in turn influence urinary and fecal continence mechanisms. The exact mechanism of SNM for the treatment of UUI and FI remains unclear and few data exist to guide which patients will respond to therapy. Further characterization of neural function of patients who undergo successful SNM may provide insight into appropriate patient selection as well as advance our understanding of pathophysiology of incontinence and SNM treatment.

A systematic review evaluating SNM in the treatment of lower urinary tract dysfunction, concluded SNM was clinically effective (>50% improvement) in 60-90% of women with UUI¹³. Similarly, a multi-center trial demonstrated SNM success rates of 90% for women with FI (>50% reduction in FI episodes)¹¹. Fecal incontinence symptoms improved in 49% of women with dual incontinence who underwent SNM primarily for UUI¹⁴.

Although SNM successfully improves UUI and FI in some women, there are no reliable predictors of successful symptoms resolution with SNM^{15,16}. Women > 55 and/or with >3 co-morbid conditions have lower UUI cure rates following SNM¹⁵, however, clinical phenotypes of women who *will* respond to SNM are unknown. Identification of quantifiable afferent neural and sphincter muscular parameters associated with successful SNM will aid patient selection as well as further understanding of pathophysiology of UUI/FI and mechanism of action of SNM in treating these disorders. This novel approach is the first to quantify objective afferent neural function with validated clinical measures and 3-dimensional ultrasound assessments of both the urethral and anal sphincters in women with dual incontinence.

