5.2. Stage I Procedure – Test Phase

Study participants will undergo a staged implant procedure as previously described^{37,38}. A quadripolar electrode (Medtronic) will be placed into the sacral foramen (confirmed with fluoroscopy) and connected via a percutaneous extension kit (Medtronic) to an external test stimulator (Medtronic) for approximately 7 days. During the test period, patients will record bladder and bowel diaries. If the number of incontinence episodes is reduced by 50% the patients will undergo placement of a permanent device, InterStim (Medtronic, Minneapolis, MN).

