# Cover Page for Data Security Plan

Sponsor Name	Northwestern University
NCT ID	NCT02357784
Sponsor Trial ID	STU00098840
Official Title of the study	Sacral Neuromodulation in Dual Incontinence: Ultrasound and Afferent Nerve Sensation Assessment (SaNDI)
Document Date	2-8-2023

Each sensory modality threshold as determined at each of the different anatomic sites will be evaluated separately. Sensory thresholds will be compared before and after SNM placement using paired t-test. Multivariate regression models will be used to determine clinical and neurophysiologic predictors of symptom improvement. Urethral sphincter volumes and presence/absence and size of internal and external anal sphincter defects will be compared in responders and non-responders.

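### The sphincter-anatomy objectives rest only on a responder split of about 15 women (1.5 to about 8 expected non-responders); a graded diary analysis should be added beside it

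*Protocol*

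**What the plan says.** Objective 2.2.2 asks for baseline sphincter anatomy to be compared between women whose sacral neuromodulation (SNM) succeeds and those in whom it fails. Item 2.2.3 adds the hypothesis that the successful group has larger muscles. Protocol section 6.1 answers both with one sentence: "Urethral sphincter volumes and presence/absence and size of internal and external anal sphincter defects will be compared in responders and non-responders". The SAP repeats it ("size of internal and external anal sphincter defects will be compared in responders and non-responders"). No test is named, responder is not defined, and no group sizes are given. The regression sentence in 6.1 covers clinical and neurophysiologic predictors and does not mention ultrasound.

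Section 6.2 sizes the study on the change in current perception threshold (CPT) alone: "we estimate that 13 subjects are needed to show a significant difference with a 80% power at 5% significance level", followed by "Assuming a 20% dropout rate, we will recruit 15 women and their partners".

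On success rates, section 1.2.2 reports that "SNM was clinically effective (>50% improvement) in 60-90% of women with UUI". It also gives 90% for FI, and FI improvement in 49% of women with dual incontinence who were treated mainly for UUI.

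The section 5.0 table schedules ultrasound at baseline and diaries at baseline, test phase and 3 months. Section 5.2 confirms the middle one: "During the test period, patients will record bladder and bowel diaries". A 50% reduction in episodes then decides implantation.

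**The concern.** A two-group comparison is only as informative as its smaller group, and the plan never checks how small that group may be. The better SNM works, the fewer failures there are to compare. At the upper success rates the non-responder group could be empty or hold one woman.

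The split also discards the size of response. A 45% reduction and no reduction both count as failure; a 50% reduction and complete dryness both count as success. Yet the diaries give a graded change before implant selection for every woman who enters Stage I and returns them.

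At stake is the reading of a null result. With so little power, a non-significant comparison could be reported as evidence that sphincter size does not matter, when it shows nothing of the kind.

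**Working it through.** **The plan's own figure.** Section 6.2 supplies the inputs. The means are given as "Assuming a mean urethral CPT of 1.3 at 250 Hz prior to treatment and a mean of 0.75 after treatment". The other inputs are an SD of 0.66, 80% power and a 5% level. Taking 0.66 as the SD of the paired difference and a two-sided test, n = [(1.96 + 0.8416) × 0.66 / 0.55]² = 11.3, so 12. The exact noncentral t gives 14 (power 0.788 at 13, 0.822 at 14). The stated 13 is thus reproduced approximately. Fifteen recruited less 20% leaves 12. None of this bears on the anatomy comparison, which has no sample-size reasoning.

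**Expected group sizes.** With success rate s, expected non-responders are N(1 − s); the number is binomial. The 75% row is a midpoint within the cited 60-90%.

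| Success | Expected, N = 15 | P(none) | P(at most 1) | Expected, N = 12 |
|---|---|---|---|---|
| 90% | 1.5 | 0.21 | 0.55 | 1.2 |
| 75% | 3.75 | 0.013 | 0.08 | 3.0 |
| 60% | 6.0 | <0.001 | 0.005 | 4.8 |
| 49% | 7.65 | <0.001 | <0.001 | 6.1 |

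At 90%: P(none) = 0.9¹⁵ = 0.206; P(one) = 15 × 0.1 × 0.9¹⁴ = 0.343; sum 0.549. With 12 women the chance of at most one is 0.66.

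**Smallest attainable p (exact tests, N = 15).** With k non-responders the floor is 2/C(15,k) for the two-sided rank-sum test and 1/C(15,k) for Fisher's test in a 2 × 2 table.
- k = 1: 2/15 = 0.133 and 1/15 = 0.067. Neither can reach 5%.
- k = 2: 2/105 = 0.019 and 1/105 = 0.0095. Both can.

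**Detectable difference (two-sided t-test, N = 15, 80% power).** Noncentrality is d/√(1/n₁ + 1/n₂) on 13 degrees of freedom. The required d is 3.14 SD with 1 non-responder, 2.31 with 2, 1.77 with 4, 1.60 with 6, and 1.57 with 7 or 8. With 12 women split evenly it is 1.8.

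**Information kept by the split.** For a bivariate normal pair this is φ(z)²/[p(1 − p)], with p the non-response proportion and z its normal quantile.
- p = 0.10: 0.1755²/0.09 = 0.34
- p = 0.25: 0.3178²/0.1875 = 0.54
- p = 0.40: 0.3863²/0.24 = 0.62
- p = 0.51: 0.3988²/0.2499 = 0.64

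**Simulated power, bivariate normal, N = 15, two-sided 5%.** The correlation r is an assumption; the documents give none.
- r = 0.6: graded 70% (Pearson) or 62% (Spearman). Split: 23%, 39%, 46% and 47% at 90%, 75%, 60% and 49% success.
- r = 0.5: graded (Pearson) 50%; split 17% at 90% success and 32% at 60%.
- r = 0.7: graded (Pearson) 88%; split 31% and 63%.

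**Simulated power with low counts.** Section 3.1.5 sets the baseline FI count at 2 in 7 days, so a woman at 2 can score only 100%, 50%, 0% or a worsening. Assume latent r = 0.6 and Poisson follow-up counts.
- Baseline 2 + Poisson(1): graded about 27-33%, split 14-22%.
- Baseline 2 + Poisson(4): graded 36-41%, split 17-28%.

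Across the shapes tried, the gain is roughly 6-20 points, and for some choices it is at the bottom of that range or below it.

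**The case against.** The strongest reply is that the plan matches its objective. Objective 2.2.2 is worded as successful against unsuccessful SNM, these are secondary aims, and no power is claimed for them. That stands. It rules out the tempting inference that the responder comparison should be replaced or reduced to description; doing so would change the question without amending the objective.

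Two further readings go too far.
- A reader might infer that one or two non-responders is what the trial should expect. That follows only at 90% success. The UUI range reaches down to 60%, and the only figure specific to dual incontinence is 49%, a nearly even split. The documents do not say whether the cited rates count women tested or women implanted. If success meant both symptoms, and they were independent, it would be 0.6 × 0.9 = 54% to 0.9 × 0.9 = 81%, or about 3 to 7 non-responders in 15.
- A reader might infer that significance is unattainable whatever the data. Section 6.1 names no test. The floors bind only for exact tests with exactly one non-responder; a t-test has no such floor.

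It is also fair to say that the normal-model contrast in power flatters the graded analysis. Diary change is discrete and capped at 100%, and the low-count results are the more sober guide.

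The regression sentence does not rescue the plan, because ultrasound is not among its named predictors. The synopsis figure of 30 subjects agrees with 15 women plus 15 partners; 30 women at 90% success would still give only 3 expected non-responders.

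**Conclusion.** The concern holds as a matter of precision. The sole planned analysis of the ultrasound measures has an unchecked smaller group of between 1.5 and about 8 expected women, and it discards graded information that is already collected. At the 90% rate it has a 21% chance of being impossible and a 55% chance of having at most one non-responder. At the balanced end it detects only very large differences, near 1.6 SD, so the weakness does not depend on the worst case.

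A graded analysis does better, but it does not make the study adequate. Under the normal model it passes 80% power only towards r = 0.7 (70% at 0.6, 88% at 0.7), and with low counts both approaches are underpowered. These power figures rest on assumed correlations and count distributions. The group-size figures rest on the success rates cited in section 1.2.2 applying to this population.

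This is something the sponsor should change, at secondary-objective weight; it does not affect the primary CPT analysis.

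**What to change.** In section 6.1 and the SAP:

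1. Keep the responder comparison for 2.2.2. State which symptom and time point define responder for this analysis, use exact tests, and report the group sizes.
2. Add a prespecified graded analysis in all women who enter Stage I and return diaries. Relate each baseline sphincter measure to the change from baseline to test phase in episodes per day, separately for UUI and FI. Use Spearman correlation or an episode-count model with the baseline count as covariate, and report 95% confidence intervals.
3. State that a null result from either analysis does not show that sphincter size is irrelevant.

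The cost is wording only: no new visit, measurement or treatment rule. The downsides are a few more exploratory estimates, and the coarseness of percentage change when baseline FI counts are as low as 2, which is why ranks or a count model are suggested.

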Sacral Neuromodulation in Dual Incontinence: Ultrasound and Afferent Nerve Sensation Assessment

(SaNDI)

PRINCIPAL INVESTIGATOR:

[name], MS
[name]
[name]
[name]
[name]
[contact]

SUB-INVESTIGATORS:

[name]
[name]
[name]
[name]

[name] [name]

Northwestern University

PARTICIPATING SITES:

Northwestern University Feinberg School of Medicine
Department of Obstetrics and Gynecology
Prentice Women's Hospital
[name]
[name]

FUNDING AGENCY:

American Urogynecologic Society

Synopsis

Title	Sacral Neuromodulation in Dual Incontinence: Ultrasound and Afferent Nerve Sensation Assessment
Short Title	SaNDI
Protocol Date	July 7, 2014
Study Duration	1.5 years
Study Center(s)	Northwestern University Feinberg School of Medicine
Objectives	
 1) To quantify the effect of sacral neuromodulation (SNM) on afferent innervation using current perception thresholds (CPT) in women with dual incontinence (urgency urinary incontinence (UUI) and fecal incontinence (FI)). 2) To identify neurophysiologic predictors of successful SNM in women with dual incontinence. 3) To quantify and compare baseline urethral and anal sphincter anatomy as assessed by ultrasound in women with dual incontinence who undergo successful and unsuccessful SNM. 4) To assess the quality of sexual relationships in women with dual incontinence and their male partners and to identify specific areas of dysfunction that are common in these patients.
Number of Subjects	30
Diagnosis and Main Inclusion Criteria	
Women with responses of at least “moderate bother” to PFDI-20 items 10 ‘do you lose stool beyond your control if your stool is loose or liquid’ and 16 ‘do you experience urine leakage associated with a feeling of urgency that is a strong sensation of needing to go to the bathroom’ will be identified through routine screening in our multidisciplinary clinic.
 
Inclusion criteria: Women over the age of 18 with idiopathic dual incontinence planning to undergo placement of a sacral nerve modulator and will be included if they have at least 5 UUI episodes on a 3-day diary and 2 FI episodes on a 7-day diary.

TABLE OF CONTENTS

Synopsis.....	2
1.0. Introduction – Background and Rationale.....	4

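### Fifteen women less the stated 20% dropout leaves 12 pairs, below the protocol's own requirement of 13, so the stated 80% power is not delivered

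*Protocol*

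**What the plan says.** Protocol section 6.2 bases the sample size on the investigators' earlier urethral CPT data, before and after drug treatment. The starting value at the 250 Hz frequency is taken as 1.3. For the follow-up value and the spread, the section gives "a mean of 0.75 after treatment with a standard deviation of 0.66". From these the protocol concludes: "we estimate that 13 subjects are needed to show a significant difference with a 80% power at 5% significance level". The next sentence turns this into a recruitment target: "Assuming a 20% dropout rate, we will recruit 15 women and their partners".

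Section 6.1 names a paired t-test for the comparison, and the SAP repeats that paragraph. The SAP gives no sample size and no dropout rate. The synopsis gives 30 against "Number of Subjects" and does not say whether partners are counted.

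**The concern.** The two closing sentences of section 6.2 do not agree. If 13 women must complete and one in five is expected to be lost, recruiting 15 does not give 13 completers.

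The comparison affected is the primary one: section 2.1 lists a single primary objective, the effect of sacral neuromodulation on CPT, and section 6.2 is the only place where the size of the study is justified. A reader who takes the 80% at face value would give a non-significant CPT result more weight than the design supports.

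**Working it through.** **Inputs, all from Protocol section 6.2 unless noted**

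- Mean before 1.3 and mean after 0.75, so the difference is 1.3 − 0.75 = 0.55.
- SD 0.66. The text does not say whether this is the SD of the paired differences or of one measurement. It is read first as the SD of differences.
- 5% significance level. Sidedness is not stated; two-sided is assumed.
- 13 evaluable women, 80% power, 20% dropout, 15 women recruited.
- Paired t-test (section 6.1 and the SAP).

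**Step 1: reproduce the 13.** The standardised effect is 0.55/0.66 = 0.833. Power of the two-sided paired t-test comes from the noncentral t distribution with n − 1 degrees of freedom and noncentrality 0.833 × √n.

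| Pairs | Exact power |
|---|---|
| 10 | 65.1% |
| 11 | 70.3% |
| 12 | 74.8% |
| 13 | 78.8% |
| 14 | 82.2% |
| 15 | 85.1% |

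The normal approximation, ((1.96 + 0.842)/0.833)², gives 11.3. Adding the usual small-sample term 1.96²/2 gives 13.2. So 13 is reproduced to within rounding, although the exact t-test needs 14 to reach 80%. A one-sided t-test (88.2% at 13) and the uncorrected normal approximation (85.2% at 13) are both well away from the stated 80%. The two-sided paired t with 0.66 as the SD of differences is the reading that fits.

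**Step 2: apply the stated dropout.**

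- Completers from 15: 15 × (1 − 0.20) = 12, which is below 13.
- Recruits needed for 13 completers: 13/(1 − 0.20) = 16.25, so 17.
- The common shortcut: 13 × 1.20 = 15.6, so 16. It reaches 15 only if rounded down.
- Largest dropout at which 15 still gives 13: 1 − 13/15 = 13.3%.
- Recruits needed for the exact-t requirement of 14: 14/0.80 = 17.5, so 18.

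If each woman independently has a 20% chance of dropping out (an assumption), the chance of at least 13 completers is 39.8% with 15 recruited and 75.8% with 17.

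**Step 3: size of the loss.** Power at 12 pairs is 74.8%, which is 80 − 74.8 = 5.2 points below the stated figure. Of this, 78.8 − 74.8 = 4.0 points come from the dropout step. The other 80 − 78.8 = 1.2 points arise because 13 itself falls slightly short under the exact test.

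**Step 4: the other reading of 0.66.** If 0.66 is the SD of a single measurement, the SD of the differences is 0.66 × √(2(1 − ρ)), where ρ is the correlation between a woman's two readings. The documents give no ρ, so a range is shown.

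| Assumed ρ | Power at 12 pairs |
|---|---|
| 0 | 46.1% |
| 0.3 | 60% |
| 0.4 | 67.0% |
| 0.5 | 74.8% |
| 0.6 | 83.6% |
| 0.7 | 92% |

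**Step 5: the synopsis figure.** If 30 means 15 women and 15 partners, nothing above changes. If it means 30 women, 30 × 0.80 = 24 pairs remain and power is about 97%, but the synopsis then gives twice the number of women in section 6.2.

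**The case against.** The arithmetic is not in dispute; the case on the other side concerns size and certainty.

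- **The gap is small.** It is one evaluable pair, or two more recruits, in a small single-centre mechanistic study with no randomised comparison. This stands, and it limits how much weight the point should carry.
- **The power figure depends on unstated choices.** At 12 pairs, power exceeds 80% with a one-sided t-test (85.5%), with the normal approximation (82.3%), or if 0.66 is a per-visit SD and the correlation is 0.6 or more. The normal approximation even asks for 12 pairs, and 12/0.80 is exactly 15, which may be where 15 came from; the protocol does not say. But section 6.2 states 13, not 12. Neither the one-sided test nor the normal approximation gives 80% at 13, and the latter overstates the power of a t-test at this size. A per-visit SD with correlation 0.6 gives 86.9% at 13, so it does not fit either. The comparison of 12 with 13 needs none of these choices.
- **Not all of the 5 points is due to dropout.** Correct: about 4 points are, as shown above.
- **The synopsis may mean 30 women.** Its eligibility text is written only for women, so this cannot be excluded. The reference to women and their partners in section 6.2 favours 15 couples. Either way the text needs correcting.
- **Twelve may itself be too many.** Sections 5.2 and 5.3 make the permanent implant conditional on the test-phase response, and section 5.4 describes payment for follow-up CPT testing for women who received it. Section 6.2 does not say whether the 20% includes women who are not implanted. If it does not, there will be fewer than 12 pairs. This adds to the concern, and it means that any restated number must say what dropout covers.

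**Conclusion.** The concern holds. On the protocol's own figures, 15 women with 20% dropout give 12 pairs, not 13, and 13 completers require 17 recruits. That part rests on no outside assumption.

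The statement that 80% power is not delivered rests on a two-sided paired t-test with 0.66 as the SD of the paired differences, which is the reading that best reproduces the stated 13. On that reading the delivered power is about 75%. The error is real but modest in size, and nothing in the SAP repairs it.

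**What to change.** Correct section 6.2 in one of two ways.

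1. **Leave enrolment unchanged and restate the power.** For example: 15 women with 20% dropout give 12 evaluable pairs and about 75% power to detect a difference of 0.55 in a two-sided 5% paired t-test, taking 0.66 as the SD of the paired differences.
2. **Keep the 80% claim and state 17 women**, or 18 if the requirement is taken as 14 pairs from the exact t calculation.

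In either case:

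- say whether 0.66 is the SD of differences or of one measurement, and that the test is two-sided;
- say whether the 20% includes women who do not go on to a permanent implant, and if it does not, lower the number of pairs and the power to match;
- make the synopsis say what its 30 counts, for example 15 women and 15 partners if that is what is meant.

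The first option costs one or two sentences and a slightly less favourable power figure. The second adds two or three women to recruitment (17 − 15 or 18 − 15). Option 1 changes no study procedure.
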